5.5. Justification for Dose

The LY2606368 monotherapy MTD when administered once every 14 days was determined to be 105 mg/m². This dose and schedule was selected as the recommended Phase 2 dose for monotherapy based on several factors including: the nonclinical LY2606368 monotherapy pharmacokinetic (PK)/pharmacodynamic model predicted exposure range for maximum tumor response coinciding with the observed clinical PK data; human pharmacodynamics simulations indicating a pharmacodynamic profile in a predicted efficacious range; and an acceptable safety profile. Please see the IB for additional details.

6. Study Population

Prospective approval of protocol deviations to recruitment and enrollment criteria, also known as protocol waivers or exemptions, is not permitted.

6.1. Inclusion Criteria

Patients are eligible to be included in the study only if they meet all of the following criteria:

- [1] have histological or cytological diagnosis of ED-SCLC (Edge et al. 2010) and have received a prior platinum-based regimen
- Cohort 1: had an objective response to prior platinum-based therapy with subsequent progression ≥ 90 days after the last dose of platinum
 - Cohort 2: either did not have an objective response to prior platinum based therapy or had progression < 90 days after the last dose of platinum

If a patient has had more than one line of platinum therapy, the platinum sensitivity should be determined from the last exposure to platinum.

- [2] have a performance status of 0 to 1 on the Eastern Cooperative Oncology Group scale (Oken et al. 1982)
- [3] have discontinued all previous treatments for cancer and recovered from the acute effects of therapy. Patients must have discontinued from previous treatments, as shown below:

Previous Treatment	Length of Time Prior to First Dose of LY2606368
Cytotoxic therapies or targeted agents that are small molecule inhibitors	≥ 14 days
Biologic agents	≥ 14 days
Immunotherapy	≥ 14 days
Radiotherapy	≥ 14 days
Major surgery, excluding biopsy	≥ 14 days

- [4] have at least 1 measurable lesion using standard techniques by Response Evaluation Criteria In Solid Tumors (RECIST) 1.1 (Eisenhauer et al. 2009)
- [5] have given written informed consent/assent prior to any study-specific procedures
- [6] are of an acceptable age to provide informed consent according to the local regulations and are at least 18 years of age

[7] have adequate organ function, as defined below:

System	Laboratory Value
Hematologic	
ANC	$\geq 1.5 \times 10^9/L$
Platelets	$\geq 100 \times 10^9/L$
Hemoglobin	≥ 8 g/dL or ≥ 5 mmol
	Transfusions to increase the patient's hemoglobin level to meet enrollment criteria are not allowed in the 14 days preceding the first dose of study drug.
Hepatic	
Direct bilirubin	$\leq 1.5 \times ULN$
ALT and AST	$\leq 2.5 \times ULN$ OR $\leq 5 \times ULN$ if the liver has tumor involvement
Renal	
Serum creatinine OR Measured creatinine clearance OR Calculated creatinine clearance (using the CKP-EPI equation - see Appendix 6)	$< 1.5 \times ULN$ OR ≥ 50 mL/min/1.73 m ²

Abbreviations: ALT = alanine aminotransferase; ANC = absolute neutrophil count; AST = aspartate aminotransferase; CKP-EPI = Chronic Kidney Disease Epidemiology Collaboration; ULN = upper limit of normal.

[8] men must be sterile or agree to use an effective method of contraception or a highly effective method of contraception during the study and for at least 12 weeks following the last dose of LY2606368

Refer to [Appendix 1](#) for definitions of fertile men, effective method of contraception, and highly effective method of contraception.

[9] women of childbearing potential must:

- have a negative serum pregnancy test at the baseline visit
- have a negative urine pregnancy test within 7 days prior to the first dose of LY2606368
- agree to use a highly effective method of contraception ([Appendix 1](#)) during the study and for 12 weeks following the last dose of LY2606368
- not be breast-feeding

Refer to [Appendix 1](#) for definitions of women of childbearing potential and postmenopausal women.

6.2. Exclusion Criteria

Patients will be excluded from the study if they meet **any** of the following criteria:

- [10] have received more than 2 prior therapies for ED-SCLC (including immunotherapy, targeted therapies, or chemotherapy)

Each line of therapy is preceded by disease progression. Discontinuation of a regimen without progression (for example, due to toxicity) or a switch of an agent within the same drug class (for example, cisplatin to carboplatin) within a regimen to manage toxicity does not define the start of a new line of therapy. Similarly, maintenance therapy (continuation maintenance or switch maintenance) will not be considered a new line of treatment.

- [11] have symptomatic central nervous system (CNS) malignancy or metastasis. Asymptomatic patients with treated CNS metastases are eligible for this study if they are not currently receiving corticosteroids to treat CNS metastases. CNS metastases should be stable for at least 14 days by clinical assessment, and patients should not have received corticosteroids to treat CNS metastases within 14 days of the first dose of study drug.
- [12] have a second primary malignancy that in the judgment of the investigator and Lilly may affect the interpretation of results
- [13] are currently enrolled in a clinical trial involving an investigational product or any other type of medical research judged not to be scientifically or medically compatible with this study
- [14] have previously completed or withdrawn from this study or any other study investigating LY2606368 or a CHK1 inhibitor or have shown hypersensitivity to any of the components of the LY2606368 formulation
- [15] have a known serious concomitant systemic disorder (for example, active infection or cardiac disease) that, in the opinion of the investigator, would compromise the patient's ability to adhere to the protocol
- [16] have a symptomatic human immunodeficiency virus (HIV) infection or symptomatic activated/reactivated hepatitis A, B, or C (screening is not required). If the medical history, symptoms, and/or laboratory values suggest that the patient may have HIV or hepatitis A, B, or C, appropriate assessment should be conducted to determine whether the patient should be excluded.
- [17] have a serious cardiac condition, such as:
- symptomatic congestive heart failure
 - New York Heart Association Class III/IV heart disease
 - unstable angina pectoris
 - symptomatic or poorly controlled cardiac arrhythmia
 - myocardial infarction within the last 3 months

- have a QT interval using Fridericia's correction (QTcF) of >470 msec on more than one screening electrocardiogram (ECG)
- a family history of long-QT syndrome

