Study I4D-MC-JTJH (JTJH) is a multicenter, Phase 2 study of LY2606368 in patients with ED-SCLC who have either platinum-sensitive or platinum-resistant/refractory disease. Cohort 1 will include patients with objective response to prior platinum-based therapy with subsequent progression ≥ 90 days after the last dose of platinum. Cohort 2 will include patients that either did not have an objective response to prior platinum-based therapy or had progression < 90 days after the last dose of platinum. Patients cannot have received more than 2 prior therapies for ED-SCLC.

Number of Patients:

Approximately 134 patients will be entered into Study JTJH, and 116 patients will be enrolled and complete the trial.

Treatment Arms and Duration:

Dose and Schedule (q 14 Days)		
Cohort	LY2606368 D1	Number of Cycles
1 and 2	105 mg/m ²	Treatment will continue until a discontinuation criterion is met.

Abbreviations: D = day; q = every.

2. Schedule of Activities

Table JTJH.2.1. Schedule of Screening Activities

Study Period		Baseline			
Cycle		BL			
Visit		0			
Duration		Up to 28 days			
Relative Day		≤28	≤14	≤7	
Procedure Category	Procedure				Comments
Study Entry/Enrollment	Informed Consent Form signed (prior to conducting any protocol specific tests/procedures)		X		
	Inclusion/Exclusion evaluation		X		
Medical History	Initial history/preexisting conditions		X		
	Historical illness		X		
	Habits assessment		X		Includes smoking history.
Physical Examination	Physical examination		X		Includes height and weight.
	ECOG performance status		X		
	Vital signs		X		
Tumor Assessment	Radiologic imaging according to RECIST 1.1		X		Baseline radiological tumor assessment per RECIST version 1.1 should be done (see Section 9.1). Radiologic assessments obtained previously as part of routine clinical care may be used as the baseline assessment provided that they were done no more than 28 days before the first dose of study drug.
	Tumor measurement (palpable or visible)		X		Performed at the same time as radiologic imaging.
Adverse Events Collection/CTCAE Grading			X		
Concomitant Medication Notation			X		
Laboratory/Diagnostic Tests	Hematology		X		
	Chemistry		X		
	Urinalysis		X		
	Coagulation		X		
	Pregnancy test	X			Women of childbearing potential must have negative serum pregnancy tests at their baseline visits and have negative urine pregnancy tests within 7 days before their first doses of LY2606368 (see Section 6.1).
	ECG		X		Single local ECG

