	Plasma biomarker sample	X				X		Collect prior to dosing on Day 1 of Cycles 1 and 3 only.
	ECG	X		X		X		Single local ECG collected at each time point. Day 1: predose, 10 min after EOI (±5 min), 30 min after EOI (±10 min), and >1 hour after EOI. Cycle 2-X: predose. However, if QTcF >480 msec is observed on Day 1, then 10 min after EOI (±5 min), 30 min after EOI (±10 min), and >1 hour after EOI should also be collected in subsequent cycles.
Optional Tumor Biopsy			X				Can occur at any time during patient's treatment.	

Study Period		Study Treatment Period						
		1		2		3-n ^a		
Cycle/Visit		14 days		14 days		14 days		
Duration		14 days		14 days		14 days		
Relative Day within Dosing Cycle		1	8	1	8	1	8	
Tumor Assessment	Radiologic imaging according to RECIST 1.1						X	For the first 52 weeks following enrollment, perform approximately every 6 weeks starting at the end of Cycle 3 (eg, Days 8-14). Thereafter, perform approximately every 12 weeks. The scanning interval (6 or 12 weeks [± 1 week]) should be maintained even if cycles are delayed. As a result, after Cycle 3, the scans may not always occur at the end of a cycle. The same method of imaging used at baseline should be used for each subsequent assessment. Scans should also be obtained as clinically indicated.
Tumor Assessment	Tumor measurement (palpable or visible)						X	Perform at least every 6 weeks starting in Cycle 3 on the same day as the radiologic imaging.
Adverse Events Collection/ CTCAE Grading		X		X		X		
Concomitant Medication Notation		X		X		X		
Lung Cancer Symptom Scale		X		X		X		The LCSS is to be administered prior to extensive interaction with site personnel and prior to administration of study drug.
Study Treatment	LY2606368	X		X		X		IV over approximately 60 (+10) min

Abbreviations: BSA = body surface area; CT = computed tomography; CTCAE = Common Terminology Criteria for Adverse Events (NCI 2009); ECG = electrocardiogram; ECOG = Eastern Cooperative Oncology Group (Oken et al. 1982); EOI = end of infusion; IV = intravenous; min = minute; LCSS = Lung Cancer Symptom Scale; PK = pharmacokinetic; QTcF = QT interval using Fridericia’s correction; RECIST 1.1 = Response Criteria In Solid Tumors Version 1.1 (Eisenhauer et al. 2009).

Table JTJH.2.3. Post-Treatment Follow-Up Schedule of Activities

Study Period		Post-discontinuation Follow-Up		
		Short-term Follow-Up	Long-term Follow-Up	
Duration		30 ± 5 days	60 ± 14 days	
Visit		801	802-X	

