5.2. Number of Patients

Approximately 116 patients (58 platinum-sensitive patients and 58 platinum-refractory/resistant patients) will be enrolled to receive LY2606368.

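### The QTcF exclusion needs more than one high screening ECG, but only one is scheduled and no repeat is required, so whether it operates depends on the site

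*Protocol*

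**What the plan says.** The last part of exclusion [17] (Protocol Section 6.2) lists, among cardiac conditions, a QTcF "of >470 msec on more than one screening electrocardiogram (ECG". The list opens with "have a serious cardiac condition, such as", so it is illustrative. Criterion [15] separately lets the investigator exclude patients who "have a known serious concomitant systemic disorder (for example, active infection or cardiac disease", if it would compromise adherence to the protocol.

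The ECG row of Table JTJH.2.1 (screening) has one entry and the comment "Single local ECG". The ECG row of Table JTJH.2.2 (on treatment) begins "Single local ECG collected at each time point. Day 1: predose" and goes on to list three post-infusion times. It then gives a conditional instruction, starting "However, if QTcF >480 msec is observed on Day 1", for extra ECGs in later cycles.

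Protocol Section 9.4.1 asks for a repeat ECG, monitoring and management when QTcF exceeds 480 msec. It also says that study-specific ECG recommendations will be supplied separately. SAP Section 5.13.6 refers to a single local ECG collected as the study schedule sets out.

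**The concern.** A confirm-on-repeat rule needs a step that produces the second reading. Here the criterion is written for at least two screening ECGs, the schedule supplies one, and nothing prompts another. A site that follows the schedule to the letter will have one reading above 470 msec, and that patient remains eligible under the QTcF bullet.

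What is at stake is safety and even handling across sites. Two patients with the same first reading can be treated differently because one site repeats the ECG and the other does not. Section 6 of the protocol rules out waivers of the enrollment criteria, which is a further reason for each criterion to be workable as written. QT prolongation is not a closed question for this drug: Section 7.7 notes that no thorough QTc study has been done.

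**Working it through.** The documents give no figure to reproduce here. The check compares the readings the bullet needs with those the schedule supplies, and then looks for any text that would supply the difference.

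**Inputs**
- Readings needed above 470 msec: at least 2, labelled as screening ECGs (Section 6.2, [17]).
- Screening ECGs scheduled: k = 1 (Table JTJH.2.1).
- Chance p that a given patient's ECG reads above 470 msec: not in the documents. It is assumed over the range 0.1 to 1.0, with readings treated as independent. This is for illustration only.

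**Probability that the bullet is met, P(at least 2 of k readings above 470 msec)**
- k = 1: 0 for every p, because one reading cannot be two.
- k = 2: p × p.
- k = 3: 3p²(1 − p) + p³.

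| p | k = 1 (as scheduled) | k = 2 | k = 3 |
|---|---|---|---|
| 0.1 | 0 | 0.01 | 0.028 |
| 0.5 | 0 | 0.25 | 0.50 |
| 0.9 | 0 | 0.81 | 0.972 |
| 1.0 | 0 | 1.00 | 1.00 |

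A repeat done only after a high first reading also gives p × p, so the rule works fully with a conditional second ECG. The zero column needs no assumption about p. The other columns show only that one repeat is enough to make the rule work.

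**Where a second reading might come from**
- *Cycle 1 Day 1 predose ECG.* Every patient has it before dosing, so two readings are scheduled before the first dose (1 + 1 = 2). It sits in the on-treatment schedule, however, and nothing calls it a screening ECG or ties it to the 470 msec limit. A predose value of 471 to 480 msec triggers no stated action. Above 480 msec, Section 9.4.1 asks for a repeat and monitoring but does not say to withhold the first dose.
- *Section 9.4.1 repeat.* It starts above 480 msec and is framed around dosing, with instructions for subsequent doses.
- *Re-screening (Section 6.4).* This follows a screen failure, and one reading above 470 msec is not a failure under this bullet. The text does not say whether ECGs from two screenings would be combined.

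**How the schedules handle comparable cases.** The pregnancy row of Table JTJH.2.1 begins "Women of childbearing potential must have negative serum pregnancy tests at their baseline visits" and goes on to state the second test that criterion [9] requires. The ECG row of Table JTJH.2.2 carries its own conditional trigger. The screening ECG row has neither kind of instruction.

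**The case against.** The best reply is that the schedule is a minimum. In Table JTJH.2.2, single plainly means one tracing at each time point, since four times are listed for Day 1. The same word in Table JTJH.2.1 therefore does not bar a repeat. Section 6.4 accepts repeated laboratory tests within screening, and the ECG is listed under laboratory and diagnostic tests. A site that sees a first reading above 470 msec and must complete the eligibility evaluation would naturally take another. The separate ECG recommendations are an obvious place for such an instruction.

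Most of this stands. A reader might infer that the bullet excludes no one. The documents do not support that: the wording points to a confirmatory repeat, many sites would do one, and nothing forbids it. What remains is that the repeat is implied and not required.

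The pregnancy-test comparison is also imperfect. Those two tests apply to every woman of childbearing potential, whereas a repeat ECG would apply only to a few patients. The trigger in Table JTJH.2.2 is the closer precedent, although it governs dosing visits and not a one-time eligibility check.

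Investigator discretion under [15] and the open list in [17] also allow exclusion, but by judgment, which a numeric limit is meant to reduce.

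**Conclusion.** The point holds as a minor one. The bullet needs at least two screening readings above 470 msec, one screening ECG is scheduled, and nothing in the protocol or SAP requires another, so its operation rests on the site's choice. This assumes that the separate ECG recommendations do not already require a repeat. They were not available, so confidence is moderate.

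No patient count should be attached. It is tempting to multiply an assumed rate by the planned enrollment, but the documents give no rate. Screening ECGs are taken in the roughly 134 patients entered, not only the 116 enrolled. The gap matters only for patients whose repeat would also exceed 470 msec, which is fewer than all those with a high first reading.

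Nor do the documents support inferring a substantial safety hazard. Section 7.7 reports no average QTcF above 480 msec, and no rise of 60 msec or more from baseline, in 101 monotherapy patients. The ORR analysis is unaffected: under the Appendix 1 definition a patient stopped before dosing is not enrolled, so does not enter the denominator.

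**What to change.** At the next amendment, add to the ECG row comment in Table JTJH.2.1: *If QTcF >470 msec, repeat the ECG during screening, before the first dose; exclude under [17] if the repeat is also >470 msec.* Criterion [17] can then stay as it is.

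If the sponsor prefers to use the Cycle 1 Day 1 predose ECG as the repeat, [17] must change too, because that ECG is not a screening assessment. It would read *on more than one ECG before the first dose*, and the new comment would drop the words *during screening*. Under this option a patient may be excluded on the planned dosing day.

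If the separate ECG recommendations already require the repeat, a cross-reference to them in Table JTJH.2.1 is enough.

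The cost is one line of text and at most one extra local ECG for the few patients with a high first reading.

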6.3. Lifestyle Restrictions

There are no specific lifestyle restrictions for this protocol.

6.4. Screen Failures

Individuals who do not meet the criteria for participation in this study (screen failure) may be re-screened. Individuals may be re-screened a maximum of 2 times. The interval between re-screenings should be at least 2 weeks. Each time re-screening is performed, the individual must sign a new informed consent form (ICF) and will be assigned a new identification number. Repeating of laboratory tests during the 28-day screening period does not constitute re-screening.

7. Treatments

7.1. Treatments Administered

Patients in both cohorts will receive 105 mg/m² LY2606368 as an approximately 60 (+10) minute intravenous (IV) infusion on Day 1 of a 14-day cycle.

The investigator or his/her designee is responsible for the following:

- explaining the correct use of the drug and planned duration of each individual's treatment to the patient/study site personnel/legal representative
- verifying that instructions are followed properly
- maintaining accurate records of LY2606368 dispensing and collection
- at the end of the study returning all unused medication to Lilly, or its designee, unless Lilly and sites have agreed all unused medication is to be destroyed by the site, as allowed by local law

7.1.1. Packaging and Labelling

The drug product, LY2606368 for injection, is supplied for clinical trial use as a lyophilized, yellow to white solid, in glass vials and is composed of either LY2606368 mesylate monohydrate and the inactive ingredient sulfobutyl ether beta-cyclodextrin sodium (Captisol®) or LY2606368 lactate monohydrate and the inactive ingredients trehalose and mannitol. [Table JTJH.7.1](#) below gives the available strengths for these 2 formulations. At the start of the study, only the mesylate monohydrate formulation will be available. However, during the study the formulation may be switched to the lactate monohydrate formulation. Sites will be notified in writing prior to this occurring. Please see the IB for additional information on these formulations.

Clinical trial materials will be labeled according to the country's regulatory requirements.

Table JTJH.7.1. LY2606368 for Injection Strengths

Formulation API	Primary Packaging (Nominal Vial size, mL)	Strength mg/vial (as free base)
LY2606368 mesylate monohydrate	50	40
LY2606368 lactate monohydrate	50	67

Abbreviation: API = active pharmaceutical ingredient.

7.2. Method of Treatment Assignment

Upon obtaining informed consent, the site will register the patient via the Interactive Web Response System (IWRS), which is accessible 24 hours a day, to assign a patient number. Patients who meet all criteria for enrollment will be assigned to receive LY2606368 in this study. The IWRS will be used to dispense LY2606368 to each patient.

7.2.1. Selection and Timing of Doses

A cycle is defined as an interval of 14 days. A delay of a cycle (Day 1) due to holiday, weekend, inclement weather, or other unforeseen circumstances will be permitted for a maximum of 7 days and not counted as a protocol deviation. An interval of at least 14 days must be maintained between LY2606368 doses, and if there is a delay the cycle length should be extended to accommodate the delay.

The actual doses of LY2606368 to be administered will be determined by calculating the patient's body surface area (BSA) at the beginning of each cycle. If the patient's weight does not fluctuate by more than $\pm 10\%$ from the weight used to calculate the prior dose, the BSA will not need to be recalculated. A $\pm 10\%$ variance in the calculated total dose will be allowed for ease of dose administration.

A patient may continue to receive LY2606368 until he or she meets 1 or more of the specified reasons for discontinuation (as described in Section 8).

7.3. Blinding

This is an open-label study.

7.4. Dosage Modification

Before the start of each cycle:

- Nonhematologic toxicities must resolve to Grade 0 or 1 or baseline, except AEs with no immediate medical consequence or those that can be controlled with adequate treatment (for example, alopecia, fatigue, nausea, vomiting, diarrhea, or asymptomatic changes in electrolytes).
- Neutropenia, thrombocytopenia, and anemia must resolve to Grade 0, 1, or 2, as shown in [Table JTJH.7.2](#).

Table JTJH.7.2. Hematologic Parameters Required for the Start of Each Cycle

	Dose
Neutrophils	$\geq 1000/\text{mm}^3$
Platelets	$\geq 75/\text{mm}^3$
Hemoglobin	$\geq 8 \text{ g/dL}$

Treatment may be delayed for a maximum of 14 days to allow a patient sufficient time for recovery from LY2606368-related toxicity. If a patient does not recover from the toxicity within 28 days from the time of last treatment, the patient should be discontinued from LY2606368. In exceptional circumstances, a longer delay is permitted upon agreement between the investigator and the Lilly clinical research physician (CRP).

If a patient, in the investigator's opinion, experiences a toxicity warranting a dose reduction, LY2606368 should be reduced as shown in [Table JTJH.7.3](#).

Table JTJH.7.3. LY2606368 Dose Reductions

Reduction	Dose
1 st LY2606368 dose reduction	80 mg/m ²
2 nd LY2606368 dose reduction	60 mg/m ²
3 rd LY2606368 dose reduction	Discontinue from LY2606368

Following a dose reduction, re-escalation is acceptable. If a subsequent LY2606368 dose reduction is again required, the patient's dose may not be re-escalated a second time.

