3.2.1. Prior Clinical Experience with LY2606368 as a Monotherapy: Study JTJA

LY2606368 was assessed as a monotherapy for patients with solid tumors and demonstrated an acceptable safety/tolerability profile, with transient neutropenia being the primary toxicity.

As of 27 August 2015, data were available from 146 patients who were treated with LY2606368 on Days 1, 2, and 3, or on Day 1 only of a 14-day schedule. The maximum tolerated dose (MTD) of LY2606368 administered on Days 1, 2, and 3 every 14 days was determined to be 40 mg/m², and the MTD of LY2606368 when administered on Day 1 every 14 days was determined to be 105 mg/m². A dose of 105 mg/m² once every 14 days was selected as the recommended Phase 2 dose for monotherapy.

In patients who have received 105 mg/m² of LY2606368, neutropenia was the most frequent and severe toxicity following treatment with LY2606368. Grade 4 decreases in neutrophils deemed related to LY2606368 treatment were observed in 71% of these patients. In general, neutrophil counts nadir on Day 8 and Grade 4 decreases were often less than 5 days. Grade 4 decreases in platelets were observed in 5.7% of patients. Grade 4 anemia was not observed. Nonhematologic toxicity occurred at a lower frequency than hematologic toxicity and was predominantly Grade 1 in severity.

In the 105 patients who received LY2606368 at a dose of 105 mg/m² once every 2 weeks, the treatment-related AEs most frequently reported following LY2606368 treatment in Study JTJA include neutrophil count decreased (93%), platelet count decreased (46%), anemia (33%), white blood cell decreased (30%), fatigue (28%), nausea (14%), febrile neutropenia (11%), and headache (11%).

Please see the Investigator's Brochure (IB) for additional information on the nonclinical and clinical experience with LY2606368.

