9.2. Adverse Events

The investigator will use Common Terminology Criteria for Adverse Events Version 4.0 (NCI 2009) to assign AE terms and severity grades.

Investigators are responsible for:

- monitoring the safety of patients in this study and for alerting Lilly or its designee to any event that seems unusual, even if this event may be considered an unanticipated benefit to the patient
- the appropriate medical care of patients during the study
- documenting their review of each laboratory safety report
- following, through an appropriate health care option, AEs that are serious or otherwise medically important, considered related to study treatment or the study, or that caused the patient to discontinue LY2606368 before completing the study. The patient should be followed until the event resolves, stabilizes with appropriate diagnostic evaluation, or is reasonably explained. Frequency of follow-up evaluation is left to the discretion of the investigator.

Lack of drug effect is not an AE in clinical studies, because the purpose of the clinical study is to establish treatment effect.

After the ICF is signed, study site personnel will record via case report form (CRF)/electronic data entry/designated data transmission methods the occurrence and nature of each patient's preexisting conditions, including clinically significant signs and symptoms of the disease under treatment in the study. In addition, study site personnel will record via CRF/electronic data entry/designated data transmission methods any change in the preexisting conditions and any new conditions as AEs. Investigators should record their assessment of the potential relatedness of each AE to study procedure or LY2606368 via CRF/electronic data entry/designated data transmission methods.

The investigator will interpret and document whether or not an AE has a reasonable possibility of being related to study treatment or a study procedure, taking into account the disease, concomitant treatments, or pathologies. A "reasonable possibility" means that there is a cause and effect relationship between the study treatment and/or study procedure and the AE.

Planned surgeries and nonsurgical interventions should not be reported as AEs unless the underlying medical condition has worsened during the course of the study.

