Appendix 2. Study Governance, Regulatory, and Ethical Considerations

Informed Consent

The investigator is responsible for:

- ensuring that the patient understands the potential risks and benefits of participating in the study
- ensuring that informed consent is given by each patient or legal representative. This includes obtaining the appropriate signatures and dates on the ICF prior to the performance of any study procedures and prior to the administration of LY2606368.
- answering any questions the patient may have throughout the study and sharing in a timely manner any new information that may be relevant to the patient's willingness to continue his or her participation in the trial

Ethical Review

Documentation of ERB/IRB approval of the protocol and the ICF must be provided to Lilly before the study may begin at the investigative site(s). Lilly or its representatives must approve the ICF, including any changes made by the ERBs/IRBs, before it is used at the investigative site(s). All ICFs must be compliant with the ICH guideline on GCP. The study site's ERBs/IRBs should be provided with the following:

- the current IB and updates during the course of the study
- the ICF
- relevant curricula vitae

Regulatory Considerations

This study will be conducted in accordance with:

- consensus ethics principles derived from international ethics guidelines, including the Declaration of Helsinki and Council for International Organizations of Medical Sciences International Ethical Guidelines
- applicable ICH GCP Guidelines
- applicable laws and regulations.

Some obligations of Lilly may be assigned to a third-party organization.

Investigator Information

Physicians with a specialty in oncology will participate as investigators in this clinical trial.

Protocol Signatures

Lilly's responsible medical officer will approve the protocol, confirming that, to the best of his or her knowledge, the protocol accurately describes the planned design and conduct of the study.

After reading the protocol, each principal investigator will sign the protocol signature page and send a copy of the signed page to a Lilly representative.

Final Report Signature

The clinical study report coordinating investigator will sign the final clinical study report for this study, indicating agreement that, to the best of his or her knowledge, the report accurately describes the conduct and results of the study.

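### Table JTJH.7.2 prints the start-of-cycle platelet minimum as 75/mm³, about 1,333 times below the entry minimum, so it cannot express the Grade 0-2 rule it is said to show

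*Protocol*

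**What the plan says.** Protocol Section 7.4 sets the conditions for starting each 14-day cycle. For blood counts the rule is: "Neutropenia, thrombocytopenia, and anemia must resolve to Grade 0, 1, or 2, as shown in" Table JTJH.7.2. The table gives three minimum values:

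- neutrophils: 1000/mm³
- platelets: 75/mm³
- hemoglobin: 8 g/dL

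The delay rule follows: "Treatment may be delayed for a maximum of 14 days to allow a patient sufficient time for recovery from LY2606368-related toxicity". A patient who has not recovered within 28 days of the last treatment should stop the drug, unless the investigator and the sponsor's physician agree on a longer delay in exceptional circumstances.

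At entry, inclusion criterion 7 (Section 6.1) requires neutrophils of at least 1.5 × 10⁹/L, platelets of at least 100 × 10⁹/L and hemoglobin of at least 8 g/dL. Section 9.2 names the grading scale: "The investigator will use Common Terminology Criteria for Adverse Events Version 4.0 (NCI 2009) to assign AE terms and severity grades". Neither document prints the platelet cut-offs of that scale.

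**The concern.** The table is presented as the numerical form of the grade rule, yet its platelet figure is on the wrong scale. A limit of 75 platelets per mm³ excludes almost nobody, so the row cannot separate Grade 2 from worse grades.

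The row is a dosing criterion checked before every cycle, and platelet toxicity is expected at this dose. In Study JTJA at 105 mg/m² (Section 3.2.1), treatment-related platelet decreases were reported in 46% of 105 patients, and "Grade 4 decreases in platelets were observed in 5.7% of patients". The same threshold bears on when a patient counts as recovered, and so on cycle delay and on the 28-day stopping rule. If sites settle the discrepancy in different ways, they will apply different platelet limits.

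**Working it through.** **Inputs**

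- Start-of-cycle minimums (Table JTJH.7.2): neutrophils 1000/mm³, platelets 75/mm³, hemoglobin 8 g/dL.
- Entry minimums (Section 6.1, criterion 7): neutrophils 1.5 × 10⁹/L, platelets 100 × 10⁹/L, hemoglobin 8 g/dL.
- Conversion: 1 L = 10⁶ mm³.

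The plan derives the figure of 75 from nothing else, so there is no calculation to reproduce. The check is a conversion to common units and a comparison of rows.

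**Step 1. Platelets in common units**

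- Printed minimum: 75/mm³ × 10⁶ mm³/L = 75 × 10⁶/L = 0.075 × 10⁹/L.
- Entry minimum: 100 × 10⁹/L ÷ 10⁶ = 100,000/mm³.
- Ratio, entry to printed: 100,000 / 75 = 1,333.

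**Step 2. The same comparison for each row**

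| Row | Entry | Start of cycle | Entry ÷ start of cycle |
|---|---|---|---|
| Neutrophils | 1,500/mm³ | 1,000/mm³ | 1.5 |
| Hemoglobin | 8 g/dL | 8 g/dL | 1.0 |
| Platelets, as printed | 100,000/mm³ | 75/mm³ | 1,333 |
| Platelets, if 75,000/mm³ | 100,000/mm³ | 75,000/mm³ | 1.33 |

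A start-of-cycle minimum below the entry minimum is not an error in itself, since neutrophils show the same pattern. What marks the platelet row is a gap of three orders of magnitude where the other two rows differ by a factor of 1.5 at most.

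**Step 3. Is it a reading artefact?** This is unlikely. The figure 75/mm³ appears in the current table and again in Appendix 7, where amendment (a) introduced the table. In both places the neutrophil row keeps its full count of 1000. The comparison sign reads differently in the two prints, and nothing here rests on that. No other section gives a start-of-cycle platelet value.

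**Step 4. Can the row express Grade 0-2?** This needs one assumption, that the lower limit of Grade 2 lies far above 0.075 × 10⁹/L. For any limit from 1 to 100 × 10⁹/L, the limit is 13 (1 / 0.075) to 1,333 (100 / 0.075) times the printed value.

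**Step 5. Does restoring the factor settle it?** Only for one value of the Grade 2 limit. Because the documents print no cut-offs, a range is assumed:

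| Assumed Grade 2 lower limit | 75,000 ÷ limit | Rescaled cell against the sentence |
|---|---|---|
| 25,000/mm³ | 3.0 | cell stricter |
| 50,000/mm³ | 1.5 | cell stricter |
| 75,000/mm³ | 1.0 | the two agree |

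With a limit of 50,000/mm³, a patient at 50,000 to 74,999/mm³ would meet the sentence and fail the rescaled table. The row ratios in Step 2 cannot settle the value: 75,000/mm³ gives 100,000 / 75,000 = 1.33 and 50,000/mm³ gives 100,000 / 50,000 = 2.0, and both are plausible in scale.

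**The case against.** The strongest reply is that this is an evident typing slip in one cell, and that the sentence above the table binds on its own. A patient with more than 75 platelets per mm³ but with Grade 3 or 4 thrombocytopenia still may not start a cycle under Section 7.4 as a whole. The grading scale is named, hematology is scheduled for Day 1 of every cycle, and Appendix 2 says: "Physicians with a specialty in oncology will participate as investigators in this clinical trial". Dose reduction and discontinuation for unacceptable toxicity remain available. All of this stands. Nothing shows that any site would dose a patient at such a count, or that sites would in fact diverge.

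It is also fair to say that the possible mismatch after rescaling depends on a cut-off the documents do not give, and that at the top of the assumed range there is no mismatch. That part is therefore conditional. It is a reason to check the corrected value against the sentence, and it does not establish a second error.

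Finally, the Study JTJA percentages describe platelet decreases at any time. They do not give counts on the day of re-treatment, so they show that the criterion is relevant without measuring how often it would be decisive.

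These points limit the likely harm. They do not make the printed threshold right, and a table added to clarify the start-of-cycle parameters should not depend on readers correcting it.

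**Conclusion.** The point holds. The platelet row is wrong in scale, with 0.075 × 10⁹/L printed against an entry minimum of 100 × 10⁹/L, a ratio of 1,333. That comparison rests on the documents alone. The conclusion that the row cannot express the Grade 0-2 rule adds only the assumption in Step 4. A lost factor of 1,000 is the likely explanation, but the documents do not establish the intended value.

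The number of doses affected cannot be estimated, because no Day 1 platelet counts are given. The response-rate decision rules, sample size, power and efficacy analyses are unaffected. The error should be fixed because it sits in an operative safety table and costs little to correct.

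**What to change.** 1. Correct the scale of the platelet cell in Table JTJH.7.2. If only the factor of 1,000 was lost, the cell should read 75,000/mm³ (75 × 10⁹/L).
2. Check that value against the lower limit of Grade 2 in CTCAE Version 4.0. If the limit is below 75,000/mm³, either print the limit in the table or amend the sentence to state the stricter platelet requirement, so that the two agree.
3. Notify sites of the corrected threshold.

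The cost is one table cell and possibly one sentence, in a protocol clarification or the next amendment, plus a site notice. Design, sample size and analysis do not change.
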